3. STUDY DESIGN

Design Overview: A two-group (n = 165/165), randomized, repeated measures design will be employed. Three hundred thirty individuals with OUD engaged in medication treatment will be recruited at one of five outpatient treatment sites: Harborview Medical Center, Country Doctor Community Health Centers, North Olympic Healthcare Network, Cascade Medical Advantage, and Evergreen Treatment Services. Enrolled patients will be individually randomized within sites to receive MABT+TAU (experimental group), or TAU alone (control). Assessments will be administered at baseline, post-intervention (3 months from baseline), and at 6, 9 and 12 months follow-up. An additional six sessions of MABT will be offered to those randomized to MABT who have continued substance use at six months.

Randomization: Following baseline data collection, participants will be randomized to treatment group by the Research Coordinator. [name], the project statistician, provided a randomization program programmed in Microsoft BASIC. Randomization will be specific to each study site and stratified by sex (approximately equal numbers of men and women assigned to each study group at each site) and baseline self-reported chronic pain. The algorithm used for randomization is a modification of a minimization method [96] based on an overall imbalance score which measures how far out of balance (within strata) the study is for a given set of random assignments. Participants will be informed of their assignment within one week of the initial appointment. Prior MABT studies showed no loss due to randomization to treatment group, thus we do not expect randomization to precipitate significant attrition. The Research Coordinator at each facility will not be blind to condition and will inform participants of their treatment condition and MABT therapist.

Measures: The outcome measures are described below (see also Table 1 in Précis).

Primary Objectives: The primary outcome is patient-reported days of illicit opioid use. Self-reported substance use is the recommended approach for intervention studies.[97] Days of illicit opioid use is defined as the number of reported days of use in last 90 days (baseline assessment) or since and including the last assessment date (follow-up assessments) in which opioids other than MAT (buprenorphine or methadone) are reported.

Time-Line Follow-Back Interview (TLFB)[3, 4] will be used to assess opioid use, other illicit drugs, and commonly abused prescription medications. Participants will be asked first to identify what substances were used. The participant will then be asked to use a calendar to retrospectively estimate their substance use, for each of the identified substances. The TLFB method was determined for alcohol, amphetamines, cannabis, cocaine, hallucinogens, opiates, sedative-hypnotics, and any psychoactive substance for time periods of 0-30 days, 0-90 days, and 0-365 days, the correlations for all substances and for the three time periods ranged from .73 to .95, demonstrating test-retest reliability and validity.[98]

The secondary outcome is days of other illicit substance use is defined as the number of days since last assessment in which cocaine, amphetamine/methamphetamine, hallucinogens, non-prescribed benzodiazepines or barbiturates, or alcohol heavy drinking days are reported using the TLFB. We will not include cannabis in this primary outcome measure due to its legal status in Washington State.

Secondary Objective Outcomes: measures of mental health (distress symptoms and emotional well-being) will include three well-validated scales for diagnostic screening: the 9-item PHQ-9 to screen for depression, the 7-item ($\alpha = .92$) GAD-7 for anxiety[8], and the Posttraumatic Stress Disorder Checklist for *DSM-5* (PCL-5),[9] which assesses symptoms of post-traumatic stress on a Likert-type scale with 20 items ($\alpha = .94$). The 4th measure, the Difficulty in Emotion Regulation Scale short form (DERS-SF)[10, 99] assesses difficulties in the modulation of emotional arousal. There are 18 items on a Likert-type scale (DERS $\alpha = .93$; DERS short form α ranges from .78 to .91 with original DERS subscales) and four subscales that assess the degree of awareness, understanding, and acceptance of emotions, and the ability to act in desired ways regardless of the emotional state. The 5th and 6th measures, the Freiberg Mindfulness Questionnaire (FMQ) with 14 items[14], and the Multidimensional Assessment of Interoceptive Awareness (MAIA)[15] with 32 items on a Likert-type scale, are used to assess skills learned in the intervention.

Physical symptoms will be assessed using the Medical Symptoms Checklist (MSC) and pain severity and interference using the Brief Pain Inventory (BPI). The MSC measures the frequency (0-8 scale) and severity (0-10 scale) of 29 common physical symptoms.[19] The BPI is a validated, widely used measurement tool for assessing clinical pain. In the U.S. it has been validated in non-cancer patients with pain[18] and HIV-infected patients.[100] The assessment includes 13 questions which provide information on pain severity and pain interference in the past week. Participants are initially asked if they have experienced any significant pain in the past week, and if they respond positively they answer subsequent

questions about duration of pain, pain severity and interference. Pain severity is rated from 0 (“no pain”) to 10 (“worst pain imaginable”), and participants are asked to rate their current pain as well as pain at its worst, at its best, and on average in the past week. Pain interference includes information on the impact of pain on general activity, walking, work, mood, enjoyment of life, relations with others, and sleep, asking the participant to rate interference on a scale from 0 (“does not interfere”) to 10 (“completely interferes”), and is reported as the mean of seven questions. Participants who responded that they had no pain in the past week will be coded “0” for pain severity and interference. The BPI will be supplemented with a single question on duration of currently reported pain in order to establish whether the pain is acute or chronic.

Opioid craving will be assessed using a single item numeric scale.[5] Participants are asked: “On a scale of 0-10, please indicate how much craving you have experienced during the past week,” with responses anchored at “0=no craving at all” and “10-strongest craving ever”. Retention will be defined as days retained in the program, or time to program discharge. Program discharges are documented in the electronic medical record (EMR) and date of discharge will be extracted from the record.

R01-Specific Objective 3 Outcomes: Exploration of the effectiveness of additional MABT dose offered at 6 months to those with continued substance use compared to those with continued substance use at 6 months in the TAU will be assessed using the Time-Line Follow-Back Interview (TLFB)[3, 4] self-reported substance use as described in in the primary objective.

For description of the intervention, see Section 2.2.

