1.2 Secondary Objectives

1) To examine the effectiveness of MABT + TAU to improve mental and physical health compared to TAU only.

Hypothesis: MABT+TAU will result in significantly improved symptoms of mental health distress (depression, anxiety, trauma), emotion regulation, interoceptive awareness and mindfulness skills, and physical health distress and pain (symptoms, pain severity, pain interference) compared to TAU only from baseline to 12 months.

2) To examine the effectiveness of MABT + TAU to positively affect substance use related outcomes of craving and treatment retention compared to TAU only.

Hypothesis: MABT + TAU will result in significantly reduced craving for opioids, and significantly longer retention (days receiving medications), compared to TAU only from baseline to 12 months.

3) To explore the effectiveness of additional MABT dose offered at 6 months to those with continued substance use (nonresponders) compared to those with continued substance use at 6 months in TAU.

Hypothesis: Among participants in both groups who are using substances at 6 months, those in MABT group who receive additional MABT sessions (between 6-9 months) will

show improved substance use at 12 months compared to those in TAU.

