Need for Behavioral Interventions to Prevent Relapse and Address Mental Health and Chronic Pain Among Patients Treated with MAT for OUD. MAT has been shown to reduce illicit opiate use and improve health outcomes for patients with OUD;[21-29] however, not all patients will benefit, as treatment retention rates are unacceptably low. Data suggests that retention may be more of a problem for patients treated with buprenorphine compared to methadone: a secondary analysis of clinical trials found that retention at 24 weeks was 46% among buprenorphine treated patients compared to 74% among methadone treated patients ($p < 0.01$).[30] Estimates of buprenorphine retention in real-world office-based settings show that approximately a half, or less, of patients who are initiated in treatment are still retained a year later.[31-34] Studies with Kaplan Meier data demonstrate a steep drop-off early in treatment with median retention ranges 3-9 months.[32, 35, 36] Clearly there is an

opportunity to intervene with patients initiating treatment with MAT to improve retention rates. The most common reason for patients to become disengaged and not be retained in care is relapse to substance use.[31] In addition, upon entering MAT, the majority (~52%) use multiple substances [37-40] and there is a high prevalence (34-57%) of co-morbid psychiatric disorders [38, 41-43] and social problems.[41, 44, 45] Post-traumatic stress disorder (PTSD) prevalence is 33-50% among patients in SUD treatment,[46] and elevated among those with opioid dependence.[47, 48]

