Physical symptoms will be assessed using the Medical Symptoms Checklist (MSC) and pain severity and interference using the Brief Pain Inventory (BPI). The MSC measures the frequency (0-8 scale) and severity (0-10 scale) of 29 common physical symptoms.[19] The BPI is a validated, widely used measurement tool for assessing clinical pain. In the U.S. it has been validated in non-cancer patients with pain[18] and HIV-infected patients.[100] The assessment includes 11 questions which provide information on pain severity and pain interference in the past week. Participants are initially asked if they have experienced any significant pain in the past week, and if they respond positively they answer subsequent questions about duration of pain, pain severity and interference. Pain severity is rated from 0 (“no pain”) to 10 (“worst pain imaginable”), and participants are asked to rate their current pain as well as pain at its worst, at its best, and on average in the past week. Pain interference includes information on the impact of pain on general activity, walking, work, mood, enjoyment of life, relations with others, and sleep, asking the participant to rate interference on a scale from 0 (“does not interfere”) to 10 (“completely interferes”), and is reported as the mean of seven questions. Participants who responded that they had no pain in the past week will be coded “0” for pain severity and interference. The BPI will be supplemented with a single question on duration of currently reported pain in order to establish whether the pain is acute or chronic.

Secondary Objective 2 Hypothesis: MABT + MAT will result in significantly reduced opioid craving, and significantly longer retention (days receiving medications), compared to TAU only from baseline to 6 months (R33) and baseline to 12 months (R01).

Opioid craving will be assessed using a single item numeric scale.[5] Participants are asked: “On a scale of 0-10, please indicate how much craving you have experienced during the past week,” with responses anchored at “0=no craving at all” and “10-strongest craving ever”. Retention will be defined as days retained in the program, or time to program discharge. Program discharges are documented in the electronic medical record (EMR) and date of discharge will be extracted from the record.

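### The craving item as quoted names no substance, so its score may mix opioid and non-opioid craving and cannot be reported as an effect on opioid craving

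*Combined protocol and SAP*

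**What the plan says.** Section 1.2 gives the craving part of the hypothesis for Secondary Objective 2 as "MABT + TAU will result in significantly reduced craving for opioids", and Section 9.1 repeats it as "MABT + MAT will result in significantly reduced opioid craving". Section 3 introduces the measure: "Opioid craving will be assessed using a single item numeric scale". On a 0–10 scale participants are asked to "please indicate how much craving you have experienced during the past week", "with responses anchored at “0=no craving at all” and “10-strongest craving ever". The same introduction, question and anchors recur in Sections 6.2.2, 6.2.4, 6.2.5, 9.1 and 9.5.2.

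Both copies of Table 1 (in the Précis and in Section 9.5.2) list the outcome as opioid craving at all five assessments. Section 9.6 analyses it under that name by GEE. On the population, Section 2.1 reports from the literature that "upon entering MAT, the majority (~52%) use multiple substances", and Section 4 expects substantial substance use co-morbidity among those enrolled.

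**The concern.** The label and the hypothesis are specific to opioids; the question put to the participant is not. Someone whose past-week craving was for methamphetamine, alcohol or cannabis can give a high score and still be answering the question as asked.

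This matters more here than in a trial with a single substance of interest, because the plan separates opioid from non-opioid use elsewhere. Section 1.1 has a hypothesis for each, Section 3 defines the two Timeline Followback (TLFB) outcomes separately, and cannabis is deliberately left out of the non-opioid outcome. Craving has no such separation, so cannabis craving could enter a score that is reported as opioid craving.

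At stake is what may be concluded about craving. A fall in general craving could be published as a fall in opioid craving, or a real fall in opioid craving could be partly hidden by craving for something else.

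**Working it through.** The point rests on comparing texts. The only stated figure that touches craving is the power for secondary outcomes, so that comes first.

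**1. The plan's own figure.** Section 9.2 states 80% power for a 0.4 SD difference on secondary outcomes. Inputs: 330 × 0.80 = 264 evaluable, or 132 per arm (Section 9.2); two-sided alpha 0.05 (stated for the primary objective, assumed to apply here); SD = 1.

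- Power = Φ(0.4 × √(132/2) − 1.96) = Φ(3.25 − 1.96) = Φ(1.29) = 0.90.
- Number per arm for 80% power: 2 × (1.96 + 0.842)² / 0.4² = 98.1, so 99.

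The stated 80% is not reproduced, but it errs on the cautious side and does not bear on this point.

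**2. Hypothesis against item.**

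| Element | Where | Names opioids? |
|---|---|---|
| Hypothesis | 1.2, 9.1 | Yes |
| Outcome label | 3, both copies of Table 1, 9.6 | Yes |
| Question text | 3, 6.2.2, 6.2.4, 6.2.5, 9.1, 9.5.2 | No, in all six |
| Anchors | The same six | No, in all six |

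I found no instruction elsewhere in the document that limits the rating to opioids. The reference cited for the scale is, by its title in Section 14, about drug craving generally, so it does not visibly supply the restriction.

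**3. Is non-opioid craving plausible in this sample?** Section 2.1 gives about 52% multiple-substance use, at treatment entry and from background literature. Table 3 in Section 4 gives past-30-day cannabis use of 37% and alcohol use of 22% in the reference programme (n = 400), with opioid use at 70% and no stimulant figure. None of these is a figure for the enrolled sample, which must be stable on medication (Section 4.1). They make mixing plausible but do not measure it.

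**4. Can the size or direction of the error be derived?** Let *m* be the share of answers that concern another substance, *d*ₒ the effect on opioid craving and *d*ₓ the effect on other craving, both in SD units, with the SD unchanged. Then

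observed effect = (1 − *m*) × *d*ₒ + *m* × *d*ₓ.

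- *d*ₒ = 0.4, *d*ₓ = 0, *m* = 0.25: 0.75 × 0.4 = 0.30 SD; power at 132 per arm = Φ(2.44 − 1.96) = 0.68.
- *d*ₒ = 0.4, *d*ₓ = 0, *m* = 0.50: 0.50 × 0.4 = 0.20 SD; power = Φ(1.62 − 1.96) = 0.37.
- *d*ₒ = *d*ₓ = 0.4: 0.40 SD for any *m*, with no dilution.
- *d*ₒ = 0, *d*ₓ = 0.4, *m* = 0.50: 0.20 SD, all of it non-opioid, yet reported as opioid craving.

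The documents give neither *m* nor *d*ₓ, so they do not choose between these cases. What holds in all of them is that the observed effect does not identify *d*ₒ unless *m* is zero or the two effects are equal.

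**The case against.** The strongest reply is that the survey form is not among the documents. Each of the six places introduces the item as a measure of opioid craving, so the protocol may quote only the stem of a question whose heading or lead-in names opioids. That stands: the defect is confirmed for the protocol text only, and the fix has to start with the form.

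A reader might infer that the item does not test the hypothesis at all, or that Secondary Objective 2 goes unanswered. The documents do not support that. Every participant is in treatment for opioid use disorder, and Section 2.2 reports that 51% of the investigators' earlier sample maintained on buprenorphine or methadone craved opioids in the past week, so an unspecific item will still pick up opioid craving. The objective in Section 1.2 speaks of craving without naming opioids; only its hypothesis narrows it. Retention, the other half of the objective, comes from the medical record and is untouched.

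A reader might also take the sample to be mostly polysubstance users. The only majority figure is the roughly 52% at treatment entry, and using several substances does not mean that a given craving rating refers to a non-opioid one.

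Finally, a reader might quote the fall in power from 0.90 to 0.68–0.37 as the cost. It cannot be used. The 25–50% share has no source. A zero effect on other craving sits badly with Sections 2.1 and 2.2, where earlier MABT samples used various primary substances and craving improved. The 0.4 SD is the plan's detectable difference, not an expected effect on craving. And the planned analysis is GEE over repeated assessments, not a two-sample test at one visit.

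**Conclusion.** The point holds as a problem of attribution. As quoted, the item leaves the substance open in all six places while the hypothesis, label and analysis are opioid-specific. If the trial is run as written, a difference between arms supports a statement about craving, not about opioid craving. No power or sample-size figure follows.

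This rests on two assumptions: that the fielded form matches the quoted wording, and that some participants' craving concerns other substances, which Sections 2.1 and 4 make plausible but do not quantify. The reach is one secondary outcome. The primary outcome, TLFB days of illicit opioid use, is substance-specific and unaffected. The change is worth making because it is cheap and alters what can be concluded.

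**What to change.** 1. Check the wording, heading and instructions of the craving item in the fielded REDCap survey.
2. If they name opioids, correct the item text in Sections 3, 6.2.2, 6.2.4, 6.2.5, 9.1 and 9.5.2. Nothing else changes.
3. If they do not, keep the present item as the analysed outcome so that the series stays continuous, but label, report and interpret it as *craving, substance not specified* in both copies of Table 1 and in Sections 9.5.2 and 9.6.
4. Add one 0–10 question on craving for opioids alongside it from the next visit on. State in Section 9.6 that this is a supporting analysis in participants who have the question at baseline.

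The hypothesis should not be moved onto the new question. Recruitment was already under way (the Version 4.0 summary says one site stopped recruiting in May 2021), so participants already enrolled would have no opioid-specific baseline for a hypothesis framed as change from baseline to 12 months. The endpoint would also change mid-trial and be confined to later entrants.

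The cost is one extra survey question, some relabelling, a narrower conclusion on craving, and an opioid-specific analysis that is only partial. Version 4.0 adds two sites, so participants still to be recruited could have the question from baseline; the documents do not say how many that would be.

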4. SELECTION AND ENROLLMENT OF PARTICIPANTS

Study Population: We plan to enroll 330 patients entering treatment for OUD at the three identified clinical sites. We expect the clinical characteristics of study subjects to be similar to those in enrolled in the SAMHSA MAT-PDOA project (see Table 3).[101] The patients at the two clinics have near equivalence in the numbers of men and women served, and age range (18 - 70 years old) with the majority (59%) under the age of 35. Most patients are white, low-income, have at most a high school education, and are on public insurance (Medicare or Medicaid), with substantial mental health and substance use co-morbidity. Approximately 25% are minorities.

Table 3. Description of Enrolled Patients in WA-MAT-PDOA Program (n=400)	
Male	55%
Age, Mean	36.9
White, Non-Hispanic	78%
Mod-Severe Depression (PHQ9>10)	67%
Mod-Severe Anxiety (GAD7>10)	62%
Mod-Severe PTSD (PCL>29)	56%

Past 30-Day:	
Cannabis Use	37%
Alcohol Use	22%
Opioid Use	70%
Illicit Rx Opioid Use	39%
Heroin Use	47%
Injection Drug Use	31%
Employed or Student	31%
Housed	91%
Criminal Involvement*	12%
*Arrests, Probation/Parole, Jailed, Sentencing	

4.1 Inclusion Criteria

Candidates for participation must meet all of the following criteria to participate in the study. Participants must be: 1) diagnosed with OUD, 2) enrolled in a medication treatment program for opioid use disorder, 3) over 18 years old, 4) enrolled and is stable in program involving (to assure medication initiation/induction has occurred) involving (if on buprenorphine) at least 4 weeks of treatment (to assure medication initiation/induction has occurred) and Rx appointments are less frequent than once/week, and (if on methadone) at least 90 days in treatment with a minimum dose of 60mg, no missed dose evaluation appointments in past 30 days, and no more than 3 missed doses in 30 days, 5) willing to forego (non-study) manual (e.g., massage) and/or mind-body therapies (e.g., mindfulness meditation) for 3 months (baseline to post-test); 6) willing to sign release for access of electronic medical records; 7) fluent in English; 8) able to attend study sessions when offered.

4.2 Exclusion Criteria

Candidates meeting any of the following criteria at baseline will be excluded from study participation. Participants must not be: 1) unwilling or unable to remain in medication treatment for OUD for the duration of the trial (includes planned relocation, pending incarceration, planned surgical procedures, etc.); 2) over 24 weeks gestation or unknown gestation, if pregnant; 3) noted by clinical or study staff as showing overt psychosis or other conditions such as cognitive impairment; cognitive impairment to be assessed with an adapted 7-item Mini-Mental Status Exam (MMSE), [102] a common screening tool in SUD treatment studies, [103] if there is questionable difficulty comprehending the consent.

4.3 Study Enrollment Procedures

Recruitment: Patients enrolling in MAT at the study sites will be recruited for study participation. Flyers with information about the trial will be distributed to clinicians and staff working with patients in medication treatment for OUD. The Nurse Care Manager(s) or

Providers at each site, who see patients in the program on a weekly basis at the start of treatment, will identify patients who meeting basic eligibility criteria, and will distribute the recruitment flyer to these participants at the time of their visit while also providing the patient with a brief overall study description and an opportunity to ask questions.

The flyer will explain that study participation involves randomization to one of two study conditions, and that one of these conditions involves receiving an 8 session intervention with a focus on body awareness, mindfulness skills, and self-care. Patients interested in study participation will be asked by the clinical staff to for permission to be contacted by the Research Coordinator (RC). The clinical staff will provide the RC with documentation with each referral that the patient meets basic eligibility criteria for study involvement (e.g. diagnosed with OUD and stable on medication dose). Based on prior intervention study experience at community SUD treatment facilities and the pilot for this study, we expect to recruit 8-12 participants per month across the sites. This recruitment rate would allow us to complete recruitment within the projected timeline. Assignment to study groups will involve stratification by sex and chronic pain (approximately equal numbers at each site) to ensure parity between men and women, and to ensure an equal distribution by group on chronic pain.

Screening: The Research Coordinator (RC) at each site will screen interested patients for eligibility in-person at the time of referral (if available) or by phone using a standardized screening script that includes acquiring verbal consent to collect preliminary screening data. On conclusion, the results of screening interview (eligibility based on inclusion/exclusion criteria, election of participation) will be entered into the screening log of the study database. Candidates who are eligible and willing to continue will be scheduled for an initial assessment visit within 14 days of the screening.

Consent and Enrollment: The initial scheduled in-person visit includes the informed consent process during which candidates will be asked to read the consent form (or if preferred, have it read to them), after which the RC will verbally reaffirm major points (participation is voluntary, potential risks, randomization protocol, etc.) and elicit and answer any questions from the candidate. If the candidate provides written consent, then the enrollment process will continue with the baseline data collection. Upon completion of the initial assessment, participants will be enrolled in the study. If at any time during this process the candidate withdraws prior to enrollment, disposition and reason for withdrawal (if obtainable) will be documented in the screening log.

Randomization: Following baseline data collection, participants will be randomized to treatment group. [name], the project statistician, provided a randomization program programmed in Microsoft BASIC. Randomization will be specific to each study site and stratified by sex (approximately equal numbers of men and women assigned to each study group at each site) and baseline self-reported chronic pain. The algorithm used for randomization is a modification of a minimization method[96] based on an overall imbalance score which measures how far out of balance (within strata) the study is for a given set of random assignments. [name], who will have no contact with study participants, programmed

the site-specific random assignment generators so that assignments become known to the Research Coordinator only upon entry of the eligibility data. Prior MABT studies showed no loss due to randomization to treatment group, thus we do not expect randomization to precipitate significant attrition. The Research Coordinator at each facility will not be blind to condition and will inform participants of their treatment condition and MABT therapist.

